8.2 Capturing and eliciting adverse event/reaction information

Participants will be asked to record local and systemic AEs for 7 days (and longer if symptoms persist at day seven, until resolution or stabilisation) following vaccination in the electronic or paper diary card (solicited AEs). Unsolicited AEs - all local and systemic AEs occurring in the 28 days following vaccination observed by the Investigator or reported by the participant, whether attributed to study medication, will be recorded in the AE section of the eCRF.

Serious adverse events (SAEs) will be followed up for the duration of the trial. Adverse events of special interest will be categorised as per CEPI guidelines (17).

Any unexpected, serious, or unusual AE following immunisation will be reported to SAEFVIC (vaccine safety surveillance service) through SAFEVAC: Integrated Vaccine Safety website that automatically forwards reports to the TGA (<https://www.safevac.org.au/Home/Info/VIC>). Adults who experience a significant adverse event reported to SAEFVIC (<https://mvec.mcri.edu.au/saefvic/>) should be referred to the Victorian Specialist Immunisation Services (VicSIS) for review and management of future COVID-19 vaccination.

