6.3 REACTOGENICITY AND SAFETY OUTCOMES

Table 4 summarises the reactogenicity and safety outcomes and relevant parameters. Further details on all collected parameters are stored in RedCAP Codebooks, as detailed in the Data Management Plan. Definitions of the terms adverse event, adverse reaction, and serious adverse event are given in the Protocol and are aligned with definitions used in trials involving investigational medicinal products.

Table 4. Reactogenicity and safety outcomes

Outcome	Parameter	Categories	Timepoints
Reactogenicity (local)	Pain		

Reactogenicity (general/systemic)	Tenderness	Grade 0, 1, 2, 3, or 4*	Day 1, 2, 3, 4, 5, 6, & 7
	Redness		
	Swelling		
	Hardness		
	Axillary lymphadenopathy		
	Warmth	Binary (presence/absence)	
	Itch		
	Fever		
Adverse Events to 28 Days	Nausea	Grade 0, 1, 2, 3, or 4*	Adverse Events to 28 Days: Day-0, -1, -7, and -28 visits, and Month-3 visit (for new information, e.g., resolution)
	Vomiting		
	Diarrhoea		
	Headache		
	Fatigue/Malaise		
	Myalgia		
	Arthralgia		
	Experienced an adverse event	Binary (yes/no)	
Adverse Reaction to 28 Days ^δ	System Organ Class [^]	As per MedDRA	Serious Adverse Events to 12 months: Unscheduled (participants instructed to contact study staff)
	Severity	Severity Grade 1 (mild), 2 (moderate), 3 (severe), 4 (life-threatening), 5 (fatal) [#]	
	Outcome	1-Resolved 2-Resolved with sequelae 3-Ongoing 4-Fatal 5-Unknown	
	Serious	Binary (yes/no)	
	Onset (days from trial vaccination)	Continuous	
	Event duration (days)	Continuous	
	Relatedness	1-Unrelated 2-Possible 3-Probable 4-Definite	

*5-point severity scale: 0-None; 1-Mild; 2-Moderate; 3-Severe; 4-Life-threatening. Refer to Protocol for more detailed definitions [#]Grade 3-4 events may be SAEs; all Grade 5 events are automatically considered SAEs. [^]Will require derivation from 'event_term' and 'saefin' fields by study team. ^δAn adverse reaction is an adverse event with causality assessment of either Possible, Probable, or Definite.

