8.2 ANALYSIS OF SECONDARY SAFETY ENDPOINTS

Table 11 specifies the secondary safety endpoints, including the timepoint measured, population measure, groups being compared and the measure of association between groups (where relevant).

Table 11. Safety endpoints

Safety Endpoint	Outcome	Timepoint	Population measure	Comparison	Measure of association
i.	Any [#] AE to Day 28 (inclusive)*	28 days post-booster	Frequency [N (%)]	Group A vs Group B	Descriptive only
ii.	Any [#] AE to Day 28 (inclusive)* [^] by severity	28 days post-booster	Frequency [N (%)]	Group A vs Group B	Descriptive only
iii.	Any [#] AE to Day 28 (inclusive)* [^] by causality assessment	28 days post-booster	Frequency [N (%)]	Group A vs Group B	Descriptive only
iv.	Any AE to Day 28 (inclusive)* by SOC and severity [^]	28 days post-booster	Frequency [N (%)]	Group A vs Group B	Descriptive only
v.	Duration [#] of AE to Day 28 (inclusive)* by SOC [^]	28 days post-booster	Median days {25 th – 75 th percentile}, min - max	Group A vs Group B	Descriptive only
vi.	Day of AE onset (days post-booster) to Day 28 (inclusive)* by SOC [^]	28 days post-booster	N by Day	Group A vs Group B	Descriptive only
vii.	AE to Day 28 (inclusive)* by Outcome ^{**^}	28 days post-booster	Frequency [N (%)]	Group A vs Group B	Descriptive only
viii.	Medically attended unsolicited AE to Month-3 visit (inclusive)	90 days post-booster	Frequency [N (%)]	Group A vs Group B	Descriptive only
ix.	SAE to study-end by SOC and expectedness [^]	Month-12 visit	Frequency [N (%)]	Group A vs Group B	Descriptive only
x.	SAE to study-end by Outcome ^{**^}	Month-12 visit	Frequency [N (%)]	Group A vs Group B	Descriptive only

[#]The Safety analysis will only include unsolicited adverse events; solicited adverse events are considered in the Reactogenicity analysis. *Adverse events within 28 days inclusive will be considered, rather than all adverse events before the Day-28 visit, which can occur between 28- and 35-days post-booster. **Outcome categories are Resolved, Resolved with sequelae, Ongoing, Fatal and Unknown; denominator is the total number of SAEs rather than the number of participants. [^]Recurrent events in the same individual will be counted as a single event (using information from the most severe occurrence); all recurrences will be included in the line list of all adverse events. [#] The duration of 'Ongoing' adverse events will be the number of days between the onset and the last visit.

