9.6 ANALYSIS OF SAFETY ENDPOINTS

Analyses for all safety endpoints will be amongst all randomised participants according to the trial vaccine received (the “Safety Population”). Recurrent events in the same individual will be counted as a single event (using information from the most severe occurrence); all recurrences will be included in the line list of all adverse events. Population measures for all safety endpoints will be reported separately by study group. Analyses of all safety endpoints will be descriptive only. Missing data on severity, onset, SOC, causality, SAE outcome, and SAE expectedness will be described by study group.

In addition, a list of all adverse events will be provided by trial vaccine including the following parameters:

- the patient identifier
- age
- sex
- adverse event (reported term, lower-level term, and SOC)
- day of onset (from Day 0)
- duration (in days)
- severity grade
- seriousness (serious/non-serious)
- special interest (yes/no)
- expectedness (yes/no)
- action taken
- outcome (Resolved, Resolved with sequelae, Ongoing, Fatal and Unknown)
- causality assessment/relatedness (*noting ‘adverse reactions’ and ‘serious adverse reactions’*)
- concomitant medication at baseline
- concomitant medication during study (prior to event)
- concomitant medication in response to event
- comorbidities at baseline
- brief narrative (SAEs only)

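### SAP Table 11 row v treats the durations of ongoing adverse events as complete, ending at an undefined last visit

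*SAP*

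**What the plan says.** Row v of Table 11 (SAP 8.2) describes AE duration to Day 28 by SOC, for Group A and Group B, as median, quartiles, minimum and maximum. For events still ongoing, the footnote states that the duration of such "adverse events will be the number of days between the onset and the last visit". It does not say which visit is meant, names no censoring method, and asks for no flag in row v.

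Four other places bear on this:
- **Status updating.** SAP 6.3, Table 4, gives the collection points for AEs to 28 days. The latest is the "Month-3 visit (for new information, e.g., resolution". Protocol 7.2.5 places the same update at the 3-month call, and Protocol 8.3 asks for follow-up to resolution where possible.
- **Timing.** SAP 4.8 plans successive analyses, the first after all participants have had the Day-28 visit. SAP 4.9 requires AE data, including outcome, up to the timepoint being analysed.
- **Recurrences.** A further footnote, marked on rows v and vi, reads: "Recurrent events in the same individual will be counted as a single event (using information from the most severe occurrence". SAP 9.6 repeats it. The same footnote adds that "all recurrences will be included in the line list of all adverse events".
- **Solicited reactions.** Protocol 8.2 has participants record these for 7 days "and longer if symptoms persist at day seven, until resolution or stabilisation". SAP Table 7 plans a distribution of reaction durations but gives no rule for computing them.

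**The concern.** The end date of an ongoing event is unknown; all that is known is that it had not ended when its status was last recorded. Entering the elapsed time as a finished duration can only shorten it. Events that start late in the 28-day window are shortened most if the cut-off is the Day-28 visit.

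Because the visit is not named, the assigned value also depends on which lock is being analysed. The same unresolved event could be reported with one duration in the Day-28 report and another in a later one, and the reader of row v could not tell which durations were complete. The reports set these summaries side by side for the two vaccines, and SOC-level counts may be small enough for a few ongoing events to matter.

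**Working it through.** The plan states no figure here, so there is nothing to reproduce. The check asks when the stated rule changes the summaries.

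**1. Duration assigned to one ongoing event.** Assigned duration = visit day − onset day. Take onset on Day 10 and nominal visit days of 28, 90 (the value in Table 11, row viii), 365 and 913:
- Day 28: 28 − 10 = 18 days
- Month 3: 90 − 10 = 80 days
- Month 12: 365 − 10 = 355 days
- Month 30: 913 − 10 = 903 days

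An event with onset on Day 27, ongoing at a Day-28 visit, is assigned 28 − 27 = 1 day.

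**2. When a quantile can change.** The rule replaces the true duration T by min(T, c), where c = visit day − onset day. A quantile changes only if some c lies below it. With onset from Day 0 to Day 28:
- Day-28 visit: c runs from 28 down to 0, so any quantile is exposed.
- Month 3: c is at least 90 − 28 = 62 days (48 if that visit falls at the early edge of its window, Day 76), so quantiles shorter than that are untouched.

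The maximum is exposed at every cut-off.

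**3. Simulation.** I used 400,000 events with onset uniform on Days 0–28. Durations were a mixture of short events (exponential with the mean shown, plus 1 day) and long ones (exponential with mean 200 days, plus 1 day). The mixtures are assumptions. Entries are lower quartile / median / upper quartile in days, with the percentage ongoing at the cut-off in brackets.

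| Short mean, share long | True | Cut-off Day 28 | Cut-off Month 3 |
|---|---|---|---|
| 5 days, 5% | 3 / 5 / 9 | 2 / 4 / 7 (24.3%) | 3 / 5 / 9 (3.5%) |
| 5 days, 15% | 3 / 5 / 11 | 2 / 4 / 8 (31.6%) | 3 / 5 / 11 (10.3%) |
| 10 days, 15% | 4 / 10 / 21 | 3 / 6 / 12 (44.4%) | 4 / 10 / 21 (10.3%) |
| 20 days, 30% | 9 / 23 / 63 | 4 / 9 / 16 (66.8%) | 9 / 23 / 62 (22.3%) |

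Month 12 and Month 30 reproduce the true quartiles. The maximum is cut at 28 days for a Day-28 cut-off and at 90 for Month 3. Leaving ongoing events out is no remedy: in the third mixture at Month 3 it gives a median of 8 against 10.

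**4. A small SOC by hand.** Take nine events: seven completed (1, 2, 2, 3, 4, 5, 7 days) and two ongoing with onset on Day 26.
- Day-28 cut-off: each ongoing event is assigned 28 − 26 = 2 days. Median 2, upper quartile 4, maximum 7.
- Month-3 cut-off, still ongoing: each is assigned 90 − 26 = 64 days. Median 4, upper quartile 7, maximum 64.
- Kaplan-Meier on the Day-28 data: S(1) = 8/9; S(2) = 8/9 × 6/8 = 2/3; two are then censored and four remain; S(3) = 2/3 × 3/4 = 1/2; S(4) = 1/2 × 2/3 = 1/3; S(5) = 1/3 × 1/2 = 1/6. Median 3, upper quartile 5.

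Censoring moves the estimates towards the later values, though nine events cannot recover them fully.

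**The case against.** The strongest reply is that the quartiles hold in the cases that look most alarming. Table 4 and the 3-month call end scheduled updating of unsolicited AEs at Month 3, so the natural meaning of the last visit is the last AE visit, not Month 30. At Month 3 or later the median and quartiles were within one day of the truth even with 22.3% ongoing. This stands. It leaves the Day-28 lock and the maximum, and it depends on a definition that the SAP does not give. SAP 1.2 notes that a previous plan covered data to Day 28, so that lock may already have been analysed. Section 4.8 of the current SAP still lists it.

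A second reply is disclosure. Row vii counts AEs by outcome, including those ongoing, and the line list (SAP 9.6) carries "day of onset (from Day 0"), duration and outcome for each event. This helps in part: row vii is not by SOC and does not sit beside row v, and the line-list duration has no separate rule for ongoing events.

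A reader might go further and infer four things that the documents do not support:
- **A 50-fold error.** The ratio 903/18 is about 50, but it contrasts the Day-28 reading with the least natural one. Between Day 28 and Month 3 the ratio is 80/18, about 4.4. Either ratio shows how loose the term is, not an expected bias. Nor is status certain to be unknown after Month 3, given Protocol 8.3.
- **Wrong onset days.** The rule for ongoing events does not touch row vi. The recurrence footnote suggests that onset is that of the worst episode, but it does not say so. It could matter only where the worst episode was not the first, and the documents give no frequency for that. One record per person is a pre-specified convention, and the line list shows every episode.
- **Reaction durations cut at Day 7.** Table 4 gives the days for grading reactions, and 4.9 lists what must be locked. Neither defines duration, and the Protocol collects later resolution. The SAP is silent, not wrong.
- **Bias between arms from unequal retention.** Nothing in the documents points to it.

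**Conclusion.** The point holds for row v. The SAP states a rule that analyses right-censored durations as observed, with an end point it does not define. Under a Day-28 cut-off the quantiles can be understated: by 1 day in the median with mostly short events (4 against 5), and more with longer ones (6 against 10, with upper quartile 12 against 21). Under a cut-off at Month 3 or later only the maximum is materially affected, and if an ongoing event sets it, it is a lower bound. These sizes rest on assumed mixtures and on onset spread evenly over Days 0–28.

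The endpoints are secondary and descriptive, so no test or effect estimate changes. It does not follow that the duration and onset summaries as a whole are wrong. The onset and solicited-reaction questions call for clarification only.

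**What to change.** In SAP 8.2, replace the rule for ongoing events:
1. Censor each ongoing event at the last contact at which its status was recorded, normally no later than the Month-3 call.
2. Report the Kaplan-Meier median and quartiles by SOC and arm where they can be estimated. Elsewhere show ongoing durations as minimum values, for example >80 days.
3. Give N (%) ongoing by SOC and arm beside row v.
4. State how events with outcome Unknown are handled, since the SAP gives no duration rule for them.

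As clarifications only:
- State whether row vi uses the onset of the first or of the most severe episode.
- State that solicited-reaction durations use the resolution information collected after Day 7 under Protocol 8.2 and at Visit 4.

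The cost is a few lines of SAP text and analysis code. Protocol 8.3 already requires onset and resolution dates. The downside is small: some quantiles will not be estimable in sparse SOCs, which is why the minimum-value display is needed.

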9 ANALYSIS OF EXPLORATORY OUTCOMES

9.1 ANALYSIS OF BREAKTHROUGH INFECTION ENDPOINTS

Breakthrough infections will be defined in three ways:

- i) Documented infections (positive by RAT or PCR)
- ii) Undocumented infections: Defined as a fold-change of ≥ 1.2 in spike-specific SARS-CoV-2 Wuhan IgG results between visits (from Day-28 onwards)
- iii) Undocumented infections identified through N-Protein IgG

Table 12 lists the breakthrough infection endpoints, including the timepoint measured, population measure, groups being compared and the measure of association between groups.

Table 12. Breakthrough infection endpoints

Breakthrough Infection Endpoint	Outcome	Timepoint [#]	Population measure	Comparison	Measure of association
i.	Breakthrough infection [^]	To Day-28 visit; Month-6 visit; Month-12 visit; Month-18, Month-24, Month-30	Incidence risk	Group A vs Group B vs Group C	Descriptive only
ii.	Breakthrough infection [^] by time-period (<14 days, Day 14 – Day-28 visit, Day-28 visit – Month-6 visit, Month-6 visit – Month-12 visit, Month-12 visit – Month-18 visit, Month-18 visit – Month 24 visit, Month-24 visit – Month 30 visit)			Group A vs Group B vs Group C	Descriptive only

[#]Analysis to be repeated at each analysis timepoint, for the risk and rate of breakthrough infection to that timepoint.

[^]Analysis to be repeated for undocumented breakthrough infections determined through Spike and N-protein IgG.

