2.2. Trial rationale and aim

Omicron subvariants have shown evidence of immune escape (10, 11) with lower neutralising antibody titres induced by vaccination and infection, requiring updated vaccines. Omicron-targeting mRNA bivalent vaccines have been introduced as boosters in many countries.

Available data show that COVID-19 vaccine effectiveness wanes considerably, although much more slowly against severe disease than infection (12). There is strong evidence that a third dose of WHO EUL vaccines provides additional protection against severe disease and these are now widely

recommended. However, the information is not yet available to determine whether a fourth dose is required, particularly in the healthy population. It is also unclear regarding the utility of additional boosters in the context of varying natural immunity, especially with high rates of previous infections. Lastly, it is not clear if mRNA bivalent vaccines are necessarily the best choice of booster for long-term repeat booster programs, particularly given their relatively high reactogenicity and rapid waning immunity. This project will compare the long-term immunogenicity of fourth doses of Moderna bivalent and Novavax boosters and a control group who do not receive a fourth dose.

The study-specific aims are to:

- Assess and compare the immune response in two randomised vaccine groups (Moderna bivalent and Novavax) at 28 days, 6-, 12, 18, 24 and 30-months post-vaccination, measured as binding antibodies.
- To assess whether a fourth COVID-19 vaccine dose provides an immunological benefit over a third dose by comparing CMI at 6, 12, 18, 24 and 30-months in a control group compared with the two vaccine groups.
- Assess the rate and severity of reactogenicity within one-week post-second booster for each group.
- Describe the frequency and severity of breakthrough infections in the vaccine and control groups up to 30 months post-vaccination.

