3.2 Outcomes

3.2.1 Primary outcomes

Immune response

Binding antibodies – These will be evaluated using the commercial Euroimmun S1 IgG ELISA (Wuhan and Omicron [once available]) on serum collected at seven timepoints (baseline, 28 days, 6 months, 12 months, 18 months, 24 months and 30 months) for the two vaccine groups and six timepoints (baseline, 6 months, 12 months, 18 months, 24 months and 30 months) for the control group. Assays will be completed within 4 weeks of sample collection for the day 28 visit.

Reactogenicity

Reactogenicity for vaccine groups (A&B) will be measured using the accepted standardised method to evaluate systemic and local side effects following vaccination using a structured questionnaire for seven days post-vaccination, as outlined in Table 1 below.

Table 1. Grading system for evaluating systemic and local side effects following vaccination (15, 16).

Local Reaction to Injectable Products^a								
	Mild (Grade 1)	Moderate (Grade 2)	Severe (Grade 3)	Potentially Life Threatening (Grade 4)				
Pain	Does not interfere with activity	Repeated use of nonnarcotic pain reliever >24 hours or interferes with activity	Any use of narcotic pain relief or prevention of daily activity	ER visit or hospitalization				
Tenderness	Mild discomfort to touch	Discomfort with movement	Significant discomfort at rest	ER visit or hospitalization				
Erythema/ redness ^b	2.5 – 5 cm	5.1 – 10 cm	>10 cm	Necrosis or exfoliative dermatitis				
Swelling ^c	2.5 – 5 cm and does not interfere with activity	5.1 – 10 cm or interferes with activity	>10 cm or prevents daily activity	Necrosis				
Hardness ^c	2.5 – 5 cm and does not interfere with activity	5.1 – 10 cm or interferes with activity	>10 cm or prevents daily activity	Necrosis				
Axillary lymphadenopathy	Does not interfere with activity	Repeated use of nonnarcotic pain reliever >24 hours or interferes with activity	Any use of narcotic pain relief or prevention daily activity	ER visit or hospitalization				
Warmth (usually reported with redness)	Absence		Presence					
Itch	Absence		Presence					
^a Grade 0 will be recorded for parameters if specific symptoms are absent.								
^b The measurement should be recorded as a continuous variable in addition to grading the measured local reaction at the greatest single diameter.								
^c Hardness and swelling should be evaluated and graded using the functional scale as well as the actual measurement.								

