6.2 IMMUNOGENICITY OUTCOME VARIABLES

Table 3 lists the immunogenicity outcome variables including the units, and participant subsets in which the outcomes are measured. There may be additional immunogenicity outcome variables (e.g. for additional variants) that may become available after this SAP is written.

Table 3. Description of immunogenicity outcome variables, including units and subsets in which they are measured

	Outcome	Subset	Units
Main study	Binding antibody (IgG) (Euroimmun Wuhan)	All	BAU/ml
	Binding antibody (IgG) (Euroimmun Omicron BA.1)	All	RU/ml
	Binding antibody (IgG) (In-house assay Omicron BA.4/5)	All	EU/ml
	Binding antibody (IgG) (In-house assay Omicron JN.1)	All	EU/ml
	Binding antibody (IgG) (N-Protein)	All	EU/ml
	Functional antibody (C-PASS assay - sVNT Wuhan)	All	U/mL
	Functional antibody (C-PASS assay - sVNT Omicron BA.1)	All	U/mL
	Functional antibody (C-PASS assay - sVNT Omicron BA.4/5)	All	U/mL
	Neutralising antibody (Wuhan)	20% of samples	NT50
CMI sub-study	Neutralising antibody (variant of concern)*	20% of samples	NT50
	IFN γ	50% of participants	IU/ml

[^]Baseline measurements are also taken at Day 0

* Variants of concern to be confirmed

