9.2 ESTIMAND-TO-ANALYSIS TABLES FOR BREAKTHROUGH INFECTION ENDPOINTS

Table 13. Generic Estimand-to-Analysis table for all breakthrough infection endpoints for incidence risk (specified in Table 12).

Exploratory objective (as per Protocol): To describe the number and severity of breakthrough cases in the control group compared with the two vaccine groups (bivalent Moderna and Novavax)	
Estimand (for each trial vaccine):	Incidence risk of [OUTCOME] [*] to [TIMEPOINT] [*] , by trial vaccine in adults 18 years or older who have received their third dose of COVID-19 vaccine at least six months previously
ESTIMAND Attributes:	Incorporation of Estimand Attribute in ANALYSIS:
Treatment Bivalent mRNA Moderna COVID-19 vaccine and protein-based Novavax COVID-19 vaccine	Study arms Bivalent Moderna vaccine arm Novavax vaccine arm Control arm
Adults 18 years or older who have received their third dose of COVID-19 vaccine at least six months previously	Analysis set All randomised participants
Variable SARS-CoV-2 infection (breakthrough infection)	Outcome measure 1. Breakthrough infection as determined by at least one positive SARS-CoV-2 test (PCR) [^]

	2. Undocumented BTI as defined as a fold-change of ≥ 1.2 in spike-specific SARS-CoV-2 Wuhan IgG results between visits
Handling of intercurrent events	
Event	Strategy⁴
Receipt of 5 th dose (self-initiated)	Treatment Policy (interpret results in conjunction with 5 th dose coverage)
Population-level summary measure	
Incidence risk (proportion positive)	

*This table is generic for all breakthrough infection endpoints for incidence risks (with varying combinations of outcomes and timepoints) specified in Table 12, as they will be analysed in the same way.

⁴Analysis to be repeated for undocumented breakthrough infections

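### The fixed 1.2-fold spike-IgG rule for undocumented infection makes detection depend on how fast each group's titres fall

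*SAP*

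**What the plan says.** SAP 9.1 gives three definitions of breakthrough infection. The first is a positive RAT or PCR. The second is "Undocumented infections: Defined as a fold-change of ≥ 1.2 in spike-specific SARS-CoV-2 Wuhan IgG results between visits (from Day-28 onwards". The third is "Undocumented infections identified through N-Protein IgG", for which no cut-off is given.

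Table 13 in SAP 9.2 repeats the spike rule for all three study arms: "Undocumented BTI as defined as a fold-change of ≥ 1.2 in spike-specific SARS-CoV-2 Wuhan IgG results between visits". N-protein is not among its outcome measures. The footnote to Table 12 does plan it: "Analysis to be repeated for undocumented breakthrough infections determined through Spike and N-protein IgG". Table 3 in SAP 6.2 lists "Binding antibody (IgG) (N-Protein" as measured in all participants.

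Table 12 reports incidence risk to each visit, and by period, for Group A versus B versus C, descriptively. Neither section gives a basis for 1.2, an assay CV, a correction for expected decline, or a rule for intervals that also contain a positive test. The direction of the fold-change is not stated; a rise is assumed here.

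Table 13 handles a self-initiated fifth dose by "Treatment Policy (interpret results in conjunction with 5 th dose coverage". A spike rise caused by such a dose is a separate matter and plays no part in the argument below.

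**The concern.** The rule looks at the net change in titre, which combines two things: the decline that would have happened anyway and the boost from infection. A fixed net threshold therefore sets a higher bar for infection where decline is steep and a lower one where titres are flat. Duration of response is one of the things this trial compares, so the infection table could partly restate the waning difference.

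Groups A and B are measured from a Day-28 post-booster sample. Controls are at least six months past their third dose at entry and give no blood at Day 28 (Protocol 4.4.1 and 7.2.4). If control titres are flatter, as one would expect, the rule flags more infections in controls at equal true risk, which favours the fourth dose.

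These tables also serve as context. SAP 4.8 treats breakthrough-infection data as needed to interpret the immunological results, and Tables 6, 9 and 10 ask for the treatment-policy estimates to be read alongside infection rates.

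**Working it through.** **No figure to reproduce.** The documents state no derivation, sensitivity or false-positive rate for the 1.2 cut-off.

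**Step 1: smallest boost flagged.** This needs no outside figure. Let w be the fold decline without infection and b the residual boost at the next visit. The observed ratio is b/w, so the rule b/w ≥ 1.2 means b ≥ 1.2 × w.

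- w = 1: 1.2-fold
- w = 2: 2.4-fold
- w = 3: 3.6-fold

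**Step 2: false flags without infection.** Assay CV is not in the documents, so it is varied. With log-normal assay error at both visits, the log ratio has SD s = √(2 ln(1 + CV²)), and the false-flag probability is 1 − Φ[(ln 1.2 + ln w)/s], with ln 1.2 = 0.182.

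| Assay CV | s | False flags per interval, w = 1 |
|---|---|---|
| 5% | 0.071 | 0.5% |
| 10% | 0.141 | 9.8% |
| 15% | 0.211 | 19.4% |
| 20% | 0.280 | 25.8% |

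At w = 2 the probability is 0.1% or less throughout this range. Over the four intervals from Month 6 to Month 30 on flat titres, a simulation in which adjacent intervals share a visit's error gives at least one false flag in 2% of uninfected people at CV 5% and 36% at CV 10%.

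**Step 3: sensitivity and apparent risk.** Assumptions, none in the documents: 20% truly infected in the interval, and log-normal residual boost with median m and log SD 0.8. Sensitivity is 1 − Φ[(ln 1.2 + ln w − ln m)/√(s² + 0.8²)]. The flagged proportion is 0.2 × sensitivity + 0.8 × false-flag probability.

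| Scenario | w | Sensitivity | Flagged |
|---|---|---|---|
| m = 3, CV 10% | 1 | 87.0% | 0.2 × 0.870 + 0.8 × 0.098 = 25.3% |
| | 2 | 60.8% | 0.2 × 0.608 = 12.2% |
| | 3 | 41.1% | 0.2 × 0.411 = 8.2% |
| m = 10, CV 5% | 1 | 99.6% | 0.2 × 0.996 + 0.8 × 0.005 = 20.3% |
| | 2 | 96.2% | 0.2 × 0.962 = 19.2% |
| | 3 | 89.8% | 0.2 × 0.898 = 18.0% |

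The true risk is 20% in every row. The direction is fixed by the rule; the size depends on boost and assay precision.

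**Step 4: would a higher cut-off cure it?** Only in part. For 2.5% false flags on a flat interval the cut-off is exp(1.96 s): 1.15, 1.32, 1.51 and 1.73 at CV 5, 10, 15 and 20%. But a cut-off k still requires a boost of k × w. At k = 2 that is 2-, 4- and 6-fold for w = 1, 2 and 3, so the ratio between groups is unchanged.

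**Step 5: Group C's first interval.** The rule starts at Day 28, where controls have no sample. Their first interval is therefore either Day 0 to Month 6 or nothing; the SAP does not say which. In neither case does it match the first interval in A and B.

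**The case against.** The strongest reply is that the size is assumed. The documents give no assay CV, waning rate, boost size or infection risk, and with large boosts and a precise assay the three flagged proportions nearly coincide. That stands, and it is why a range is shown.

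The consequence is also limited. The endpoint is exploratory, descriptive and without a measure of association. RAT/PCR and N-protein versions are planned beside it, and nothing shows the 1.2 rule entering the primary or secondary endpoints; SAP 4.9 records infections by date of positive test. Group C is non-randomised and under 60, so comparisons with it are open to confounding anyway. All of this stands, but none of it removes the dependence on waning.

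Some stronger readings are tempting but not supported:

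- **That Group A wanes faster and will look better protected than B.** Protocol 2.2 questions mRNA boosters, "particularly given their relatively high reactogenicity and rapid waning immunity", but gives no rate, and Protocol 2.1 says the comparative duration for the protein vaccine is unknown.
- **That 1.2-fold lies within assay noise.** This is conditional: at CV 5% false flags are 0.5% per flat interval.
- **That separate assay runs create false infections.** The statement "Assays will be completed within 4 weeks of sample collection for the day 28 visit" bears only on Day 28 to Month 6 in A and B, where false flags are near zero once titres halve. Batching of later and control sera is not described.
- **That N-protein was left out or ranked last.** The Table 12 footnote plans it, and the list in 9.1 states no ranking. What is missing is a cut-off and an entry in Table 13.
- **That documented cases will be counted twice.** The class name suggests otherwise and no pooled total is planned. The wording simply does not exclude them.

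**Conclusion.** The concern holds as a structural flaw in an exploratory definition. A single uncorrected net threshold makes detection depend on each group's decline: the required boost is 1.2 × w, which is arithmetic from the SAP's own rule. The likeliest distortion is between A and B together and the controls, because only A and B are measured from a post-booster peak. No direction can be given for A against B.

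The size is uncertain. With 20% infected and a boost log SD of 0.8, flagged proportions at w = 1, 2, 3 run from 25%, 12%, 8% (3-fold boost, CV 10%) to 20%, 19%, 18% (10-fold boost, CV 5%). False flags per flat interval run from 0.5% at CV 5% to 26% at CV 20%. The primary analysis is not affected. The change is worth making because the table invites a three-group comparison that the rule cannot support evenly.

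**What to change.** In SAP 9.1 and Tables 12 and 13:

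1. Add N-protein IgG to Table 13's outcome measures, with a cut-off fixed before unblinding, and use it as the lead serological definition in between-group tables. State that some infections may not raise N-protein IgG.
2. Keep the 1.2-fold spike rule as a secondary definition. Show it beside a higher threshold set from the assay's own repeatability, for example 2-fold, which is also the rise Protocol 11.3.1 requires for seroresponse when baseline is at least 200 BAU/ml. Report the spike rule's sensitivity in documented cases by group. Do not use it to compare A, B and C over Day 28 to Month 6. Say that a higher threshold cures only false flags, not the dependence on waning.
3. Count an interval as undocumented only if it contains no positive RAT or PCR. Table 13 names only PCR for documented infection where 9.1 names RAT or PCR; align the two.

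The cost is SAP wording and some reordering of planned tables. N-protein IgG is already listed for all participants, so no new sampling or assay is needed. The price is that infections without an N-protein response drop out of the lead table, which is why the spike rule stays as a second view.
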